Aim 3: *To determine the efficacy of targeted kudzu versus placebo in reducing alcohol-associated sexual risk behaviors and incidence of STIs*, by treatment arm, we will use GEE Poisson models with robust standard errors for the four monthly ACASI assessments on numbers of sex partners, HIV-serodiscordant condomless sex partners, condomless sex partners while intoxicated with alcohol, and condomless sex events with serodiscordant partners, including the baseline value. In the event that these outcomes are severely over-dispersed, we will analyze indicators for any self-report of each behavior, using GEE logistic models. We will use GEE logistic regression models to evaluate differences in incidence of STIs between kudzu and placebo arms over time. Incidence will be evaluated as a composite outcome (i.e., any incident STIs), as well as by type (i.e., incident syphilis, gonorrhea, or Chlamydia), and, for gonorrhea and Chlamydia, by site (i.e., urethral, oral, vaginal, or rectal). MDEs: Based on estimates of within-subject correlation and control prevalence from our Project Echo trial, we estimate that the study will have 80% power to detect 32% reductions in numbers of male anal sex partners, 59% reductions in serodiscordant condomless anal sex partners, 48% reductions in condomless anal sex partners while intoxicated with alcohol, and 58% reductions in condomless anal sex events with serodiscordant partners in the treatment arm. In analyses using GEE logistic models, we will have 80% power to detect reductions of 15% for any male anal sex partners, 39% for any HIV-serodiscordant condomless anal sex partners, 40% for any condomless anal sex partners while intoxicated with alcohol, and 31% for any condomless anal sex events with serodiscordant partners in the treatment arm. After accounting for expected loss to follow-up, we will have an estimated 80% power in 2-sided tests with a type-I error rate of 5% to detect reductions of 23-26 percentage points in the incidence of STIs at month 3, depending on the control rates, assumed to be in the range 30-40%, and within-subject correlation of these outcomes, assumed to be 0.1 to 0.3; both inputs were based on data in an ongoing PrEP demonstration project.

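### Aim 3 gives two detectable reductions, 39% and 31%, for fallback indicators that coincide unless the Project Echo items differ in an unstated way; separately, all eight behavioural figures are for anal sex while the modelled outcomes are not

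*Combined protocol and SAP*

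**What the plan says.** Section 1.7, Aim 3, plans GEE Poisson models "for the four monthly ACASI assessments on numbers of sex partners" and three related counts, baseline included. The full list of outcomes is "numbers of sex partners, HIV-serodiscordant condomless sex partners, condomless sex partners while intoxicated with alcohol, and condomless sex events with serodiscordant partners". If these are severely over-dispersed, "we will analyze indicators for any self-report of each behavior, using GEE logistic models".

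The detectable effects are introduced with "Based on estimates of within-subject correlation and control prevalence from our Project Echo trial". No prevalence or correlation value follows. Eight behavioural figures are given at 80% power:

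| Outcome as worded in the power statement | Count model | Yes/no fallback |
|---|---|---|
| Male anal sex partners | 32% | 15% |
| Serodiscordant condomless anal sex partners | 59% | 39% |
| Condomless anal sex partners while intoxicated | 48% | 40% |
| Condomless anal sex events with serodiscordant partners | 58% | 31% |

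The two fallback figures at issue read "39% for any HIV-serodiscordant condomless anal sex partners" and "31% for any condomless anal sex events with serodiscordant partners in the treatment arm".

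Section 1.2 lists Aim 3 among four primary objectives. Section 1.4.d admits participants on anal or vaginal sex and gives a binge threshold for women. Section 1.5.d stratifies randomization by gender. Aim 3 also analyses vaginal-site infections.

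**The concern.** **The fallback pair.** In a given period, a participant has at least one serodiscordant condomless anal sex partner exactly when at least one condomless anal sex event with such a partner took place. The counts differ, because one partner can account for several events, so 59% and 58% do not conflict. The any/none indicators do not differ. One variable has one control prevalence and one within-subject correlation, and therefore one detectable reduction at 80% power. The plan takes both from the same survey schedule and the same source trial, yet reports 39% and 31%.

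**The outcome mismatch.** All eight figures are worded for anal sex and two of them for male partners: "32% reductions in numbers of male anal sex partners" and "reductions of 15% for any male anal sex partners". The models carry neither restriction, and the plan does not say how the anal-sex inputs carry over.

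**What is at stake.** If the fallback is used and the serodiscordant indicator shows no effect, a reader cannot tell whether the trial had 80% or roughly 60% power for a 31% reduction. On the second limb, the plan states no power for the behavioural outcomes that it will actually model.

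**Working it through.** **Inputs from the plan.** 120 randomized 1:1, so 60 per arm; 80% retention, so 0.80 × 60 = 48 per arm; 80% power; four monthly surveys including baseline, so three after baseline.

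**Inputs assumed.** Two-sided 5% (stated for other outcomes, not restated for these eight); 48-60 per arm; 1-4 visits; exchangeable correlation ρ from 0.1 to 0.7; reductions read as relative reductions in prevalence.

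**Can the plan's figures be reproduced?** Not forwards, because the Project Echo prevalence and correlation are not given. As a check on the method, the STI figure in the same aim does have a stated range of control rates. With 48 per arm, the two-proportion formula gives a detectable difference of 22.1 points at a control rate of 30% and 25.2 points at 40%, against the stated 23-26. The method is within about one point and slightly less conservative than the plan's own.

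**Formulas.** Effective n per arm = n·m / (1 + (m−1)ρ). With control prevalence p and reduction r, let q = p(1−r) and p̄ = (p+q)/2. Then

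power = Φ( [ (p−q) − 1.96·√(2p̄(1−p̄)/n) ] / √( [p(1−p)+q(1−q)]/n ) ).

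**Worked case: 48 per arm, 3 visits, ρ = 0.3.** Effective n = 144/1.6 = 90.

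- Solving for 80% power at r = 39% gives p = 0.526: q = 0.321, difference 0.205, standard errors 0.0737 (null) and 0.0721 (alternative), power 0.80.
- At the same p and r = 31%: q = 0.363, difference 0.163, standard errors 0.0741 and 0.0731, power 0.597.
- Solving for 80% power at r = 31% gives p = 0.664. At that p, power for 39% is 0.943.

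**Over the whole grid, pooled and unpooled variance.**

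| Quantity | Range |
|---|---|
| Control prevalence implied by 39% | 0.33-0.72 |
| Control prevalence implied by 31% | 0.45-0.83 |
| Gap between them at equal n, m and ρ | 0.117-0.139 |
| Power for 31% if the inputs behind 39% hold | 0.589-0.607 |
| Power for 39% if the inputs behind 31% hold | 0.935-0.948 |

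A simulation with 48 per arm, 3 visits, beta-binomial data and a robust Wald test on the log odds ratio (4,000 runs each) gave 0.78-0.80 for 39% and 0.58 for 31%.

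**Other readings of the percentages.** As percentage points, the largest detectable difference found was about 28 points (effective n = 48), so neither 31 nor 39 fits. As odds reductions, the highest power found at 48 per arm was 56% for 39% and 36% for 31%. Neither reading rescues the pair.

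**What would reconcile the pair if the items do differ** (48 per arm, 3 visits):

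- Prevalence alone: a gap of 12-14 points.
- Correlation alone: at p = 0.58, ρ = 0.46 (effective n = 75) gives 80% power for 39%, and ρ = 0.10 (effective n = 120) gives 80% for 31%.
- Both: p = 0.526 with ρ = 0.30 fits 39%, and p = 0.604 with ρ = 0.15 fits 31%.

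A shorter recall window for events alone would work the wrong way, since lower prevalence raises the detectable reduction (ρ = 0.3: 29% at p = 0.70, 41% at 0.50, 48% at 0.40). A longer event window or a shorter partner window would work in the needed direction.

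**Outcome mismatch.** No arithmetic applies. Neither the anal-sex share of the modelled behaviour nor the gender mix of the sample is given.

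**The case against.** The strongest reply is that both figures rest on Project Echo items that the documents do not show. The plan gives the survey schedule but no recall window. Table 3 lists event-level data on recent episodes of sex separately from counts of partners and acts, so the two indicators may come from separately answered items. A modest difference in prevalence, correlation or both would then reconcile them. This stands: it makes the conflict conditional. It does not remove it, because the plan states no such difference and gives no input from which a reader could infer one.

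Three stronger readings are tempting and not supported. A reader might infer a proven arithmetic error; neither figure can be recomputed from the documents. A reader might infer that 39% is the correct figure because it is the less favourable; the documents do not allow a choice. A reader might infer that the trial is too small; nothing ties the 120 participants to Aim 3, the plan nowhere says that it expects a 31% effect, and it describes the trial as a pilot.

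On the second limb, the plan names its source trial and labels each figure as anal sex, so it hides nothing. Recruitment through LGBT venues and apps (section 1.4.b) may make the inputs fit much of the sample. Both observations stand, and they are why no size or direction can be put on the mismatch. They do not supply power for the outcomes modelled.

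**Conclusion.** Both limbs hold, within limits. The 39% and 31% cannot both apply to one indicator. If the two indicators are one variable, the choice of inputs decides whether power for a 31% reduction is 80% or about 59-61% (0.58 by simulation), and whether power for 39% is 80% or about 94-95%. This rests on the assumed ranges for visits, correlation and numbers per arm, and on the indicators sharing a recall period. The ranges matter little, since the power figures barely move across the grid. The conflict bears only on the conditional logistic fallback.

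The anal-sex wording is a mismatch between what was powered and what will be analysed, of unknown size and direction. Neither limb changes a test, an endpoint or the sample size. The point is worth correcting because Aim 3 is a stated primary objective and the correction is cheap. Confidence is medium, because the Project Echo items are unseen.

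**What to change.** 1. Check the two serodiscordant indicators against the Project Echo items. If they are the same variable, replace the pair with one detectable effect recomputed from one prevalence and one correlation; until that is done, do not claim 80% power for a 31% reduction. If they differ, state how (wording, recall window or handling).
2. State the item definition, control prevalence and within-subject correlation behind each behavioural figure.
3. Recompute the behavioural detectable effects for the outcomes actually modelled, or state that they apply only to anal-sex outcomes and that power for the modelled outcomes has not been established.

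The cost is recalculation and wording in section 1.7. No participants, models or endpoints change. Some stated figures may become less favourable.

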1.2 Specific Aims

The primary objectives of this study are as follows:

1. To determine the efficacy of targeted kudzu versus placebo in reducing binge drinking, as determined by number of binge drinking days in timeline follow-back (TLFB), by treatment arm.
2. To determine the efficacy of targeted kudzu versus placebo in reducing recent alcohol consumption, as determined by the proportion of ethyl glucuronide (EtG) positive urines, by treatment arm.
3. To determine the efficacy of targeted kudzu versus placebo in reducing alcohol-associated sexual risk behaviors and incidence of STIs, as determined by audio computer assisted survey instrument (ACASI) data and STI (syphilis, *Neisseria gonorrhoea*, *Chlamydia trachomatis* testing, HIV) testing, by treatment arm.
4. To evaluate the tolerability and acceptability of targeted kudzu versus placebo, as determined by adverse clinical event rates and medication adherence (via data from MEMs cap dispenser monitoring and self-report from SMS texts and TLFB), by treatment arm.

1.3 Facilities and Investigator.

Study activities will take place at the Center on Substance Use and Health (CSUH) of the San Francisco Department of Public Health (SFDPH), a well-established clinical trial site. [name] has a joint appointment as a Senior Research Scientist at SFDPH. He has conducted research at this field site since 2008. The site is centrally located near multiple transit lines with convenient access for residents of multiple neighborhoods with high rates of alcohol use. We have had remarkable success recruiting and retaining alcohol and substance users at this location. Study staff have access to both **SFDPH** and **University of California, San Francisco**. The paired effort of these institutions has proven highly effective in both research and clinical care in San Francisco.

1.3.a. Form 1572

See Appendix B

1.3.b. Sponsor-Investigator

[name], MPH (See Appendix C for CV)

1.3.c. Sub-Investigator

[figure not shown]
[name] (See Appendix D for CV)

1.3.d. Form FDA 3454

See Appendix E

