1.4 Study Design

This study is a double-blind, placebo-controlled, two-arm trial in which 120 binge drinkers with AUD will be randomly assigned to receive 12 weeks of kudzu or placebo, to be taken on an as-needed basis (see Figure 2) with 1- and 3-month post-treatment follow-up visits. This efficacy study will enroll sexually active, binge drinkers with AUD because they are the most likely population to benefit from this intervention by limiting harms associated with heavy alcohol use and decreasing alcohol-related sexual risk behaviors. A study clinician will perform the Structured Clinical Interview for the DSM-V (SCID) to screen for AUD and determine eligibility. Upon enrollment, 120 participants will be randomized 1:1 to kudzu extract (2 grams) or placebo for targeted administration. Participants will be seen weekly for behavioral surveys, urinalyses, study drug dispensing, and alcohol use counseling. Safety laboratory assessment, vital signs, and the audio computer assisted survey instrument (ACASI) will be completed monthly. Efficacy, tolerability, and acceptability (Specific Aims 1-4) will be assessed upon trial completion as measured by number of binge drinking occasions and numbers of drinks on drinking days via timeline follow-back at weekly visits; number of EtG-positive urine samples; sexual risk behavior data through monthly surveys via ACASI; frequency of adverse events; and cumulative medication adherence data at week 12. Durability of intervention effects will be evaluated at 1- and 3-month post-treatment visits.

1.4.a. Study Participants, recruitment, and inclusion/exclusion criteria. We will recruit a total of 120 racially/ethnically diverse sexually active, binge drinkers with AUD will be enrolled in the study. Subjects will be San Francisco Bay Area residents between 18-70 years of age. The project is designed specifically for binge-drinkers at high risk for HIV transmission or acquisition.

1.4.b. Recruitment.

For this study, we will combine several strategies that have proven successful in our previous studies with alcohol- and substance-using individuals:

Advertisements: We will run advertisements in the local papers catering to the community and widely read by our participants.

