Internet recruitment: As in our current studies, Internet-based recruitment will occur through strategic placement of banner ads on Web sites frequented by alcohol-using individuals, including craigslist.org, Facebook, manhunt.net, Adam4Adam.com, BarebackRt.com and tweaker.org, and on smart phone mobile applications for this population, including Grindr, Instagram, Manhunt Mobile, and BarebackRt Mobile. Additionally, we will use targeted ads for San Francisco Bay Area on Facebook and Google Adwords.

Active recruitment: We will recruit on the street in neighborhoods and at fairs frequented by alcohol-using individuals, collecting phone numbers of interested potential participants, and leaving cards and fliers in LGBT meeting places, local community-based organizations (CBOs), bars, and clubs. We will also recruit at clinics with many alcohol-using patients such as the Health Department's STD clinic (City Clinic) and the public HIV clinic at San Francisco General Hospital (SFGH).

Snowball sampling: Study participants are encouraged to refer their friends by taking cards and fliers so that potential participants can call us. This is a method to reach some people we may miss via our other recruitment strategies.

In addition, we will also recruit participants that screen ineligible for our other ongoing NIH-funded studies. Prospective and former participants from our ongoing trials will be asked if they are willing to be contacted for future studies; participants who provide consent will have their contact information saved in a database for future contact. Once this study is running, potential participants will be triaged with a pre-screening process that directs them to the study for which they are most likely to be eligible, an approach we have found to be effective and efficient for our parallel methamphetamine trials.

1.4.c. Retention.

We have a proven record of high retention rates in our studies, including among alcohol-using MSM. We anticipate an 80% retention rate over the 12 weeks of follow-up for this study. While we realize that retention among substance users is considerably challenging, we believe our goal is realistic and feasible. We acknowledge, however, that extra efforts will be needed to ensure

that our study participants adhere to the study protocol, and we will make every effort to meet and hopefully exceed our retention target.

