AE Reporting. Each AE will be classified by the study clinician as serious or non-serious, and appropriate reporting procedures will be followed; these decisions will be reviewed on a real-time basis by the study clinicians. An AE is defined as any reaction, side effect, or untoward event that occurs during the course of the clinical trial, whether or not the event is considered medication-related. A new illness, symptom, or worsening of a pre-existing condition or abnormality is considered an AE. Stable chronic conditions that are present prior to clinical trial

entry and do not worsen are not considered AEs. For this study, AEs will include symptoms reported by the patient and abnormal measures of clinical importance noted by study staff.

Study staff will assess participants for any medical or psychiatric side effects by asking the participant "How have you been feeling since I saw you last?" Study staff will also review the previous AE form and inquire whether any of those events are continuing. Study clinicians will follow all AEs, regardless of severity, until resolution or until four weeks following completion of the trial. Each new or unresolved AE will be recorded on the AE case report form according to standard procedures. All AEs will be assigned a severity (mild, moderate, severe or life-threatening), as defined by the DAIDS Table for Grading Severity of Adult Adverse Experiences for HIV Prevention Trials. 148 The study clinician will review the information and offer an educated opinion about the relatedness of the event to the study drug. These data will be reviewed by the PI or Co-Investigator on a weekly basis.

A summary report of all AEs (including SAEs) will be prepared at least every six months (frequency determined by our IRB, DSMB, and NIH), to be submitted to the DSMB, IRB and NIH.

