***Aim 4:** To evaluate the tolerability and acceptability of targeted kudzu versus placebo*, as determined by adverse clinical event rates and medication adherence (via data from MEMs capmonitoring and self-report from EMA and TLFB), by study arm. While laboratory studies have demonstrated the tolerability and acceptability of daily kudzu, we will examine these outcomes in an outpatient setting for targeted (prn) dosing. Adverse clinical events (AEs) and other binary safety outcomes will be presented as percent of participants that experience the safety outcome by treatment arm. Binary adverse effect measures will be analyzed using exact methods, since they are expected to be uncommon. We will measure the acceptability of kudzu among participants by determining medication adherence via MEMs cap opening events, pill count and self-report. Adherence measures of interest will include percent of doses taken during reported drinking days, patterns of adherence and time to stopping medication. We will assess how these measures of adherence track with patterns of alcohol use and binge drinking as reported in TLFB. GEE logistic models will be used to estimate the proportions of kudzu participants taking medication during periods of reported alcohol use and binge drinking. Concordance of adherence measures based on MEMs cap and self-report measures will be examined using weighted Kappa and correlations.

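### Aim 4 compares adverse events only as the percentage of participants ever affected; an event rate per person-week with a 95% CI should be reported beside it

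*Combined protocol and SAP*

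**What the plan says.** Section 1.2 lists tolerability and acceptability among four primary objectives, "as determined by adverse clinical event rates and medication adherence". Section 1.4 names the frequency of adverse events among the measures assessed at trial completion.

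Section 1.7, Aim 4, gives the only analysis of adverse events (AEs): "Adverse clinical events (AEs) and other binary safety outcomes will be presented as percent of participants that experience the safety outcome by treatment arm". It continues: "Binary adverse effect measures will be analyzed using exact methods, since they are expected to be uncommon". No exact test is named. No event count, person-time, rate model or confidence interval is specified for AEs.

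Section 1.1.c defines AEs broadly: "An AE is defined as any reaction, side effect, or untoward event that occurs during the course of the clinical trial", whether or not related to the medication. It adds: "A new illness, symptom, or worsening of a pre-existing condition or abnormality is considered an AE". The same section has AEs elicited and documented every week. Table 3 schedules self-reported AEs at enrollment and monthly.

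**The concern.** A summary of ever versus never affected gives the same score to a participant with one mild headache and to one with an event every week. It also ignores how long each participant was observed. When AEs are elicited weekly under a definition this wide, repeat events may carry much of the information about tolerability.

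GEE Poisson models with robust errors are already planned for the drinking counts (Aim 1) and the sexual behaviour counts (Aim 3), but not for AE counts. Tolerability is a primary objective. An exact test with little power and no interval gives the reader no means of telling a well-tolerated product from a comparison that could not have shown a difference.

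**Working it through.** **No figure to reproduce.** The plan states no AE rate, power or detectable difference for Aim 4. The nearest check is the Aim 3 STI figure: a detectable reduction of 23-26 percentage points at control rates of 30-40%. With 60 × 0.8 = 48 per arm, the two-proportion normal formula gives 22.2-25.2 points and exact Fisher power gives 23.3-26.6. The inputs below are therefore broadly in line with the plan's own, although its within-subject correlation was not modelled.

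**Inputs from the documents**
- Section 1.4: "120 participants will be randomized 1:1 to kudzu extract (2 grams) or placebo for targeted administration", so 60 per arm.
- Section 1.4.c: "We anticipate an 80% retention rate over the 12 weeks of follow-up for this study".
- Test level: "80% power in 2-sided tests with a type-I error rate of 5" percent, stated for Aims 1 to 3 and assumed here for Aim 4.

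**Assumptions**
- Fisher's test stands for the unnamed exact method.
- The AE event rate on kudzu is 1.5 times that on placebo.
- The placebo rate is 0.05-0.2 AEs per person-week, which is 0.6-2.4 over 12 weeks.
- Rates vary between participants with a coefficient of variation (CV) of 0.5-1.0, so k = CV² = 0.25-1.

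**Formulas without dropout.** Let μ be the mean AEs per placebo participant over 12 weeks.
- P(ever affected) = 1 − (1 + kμ)^(−1/k), or 1 − exp(−μ) when k = 0. Fisher power follows by enumerating all outcomes.
- SE(log rate ratio) = √[(1/μ + 1/(1.5μ) + 2k)/n].

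**Worked case, μ = 1, k = 0.5, n = 60**
- Ever affected: 1 − 1.5⁻² = 55.6% on placebo and 1 − 1.75⁻² = 67.3% on kudzu. Fisher power is about 21%.
- Event rate: SE = √[(1 + 0.667 + 1)/60] = 0.211; log 1.5 = 0.405; 0.405/0.211 = 1.92. Power = Φ(1.92 − 1.96), about 49%.

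**Simulation with 20% loss in each arm, rate ratio 1.5, CV 0.5-1.0**

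| Placebo AEs per person-week | Fisher, ever/never | Robust rate ratio |
|---|---|---|
| 0.05 | 13-22% | 30-39% |
| 0.1 | 14-20% | 40-59% |
| 0.2 | 12-15% | 48-80% |

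With no true difference and equal dropout, Fisher rejected in 2.6-3.3% of trials and the rate test in 4.3-5.2%.

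**Bounds**
- For a 50% higher event rate, Fisher power with 60 per arm never exceeds 34% at any placebo rate (k = 0). The maximum is 21% at k = 0.5 and 16% at k = 1.
- At μ = 0.02, matching the 2.0% placebo incidence cited in section 1.1.b from an earlier isoflavone trial, power is 0.3% for Fisher and 5% for the count.
- At k = 1 the count analysis never reaches 80% power, whatever the event rate.

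**The case against.** **A reader might infer that the AE definition makes events common.** The documents do not establish that. They give no any-AE rate, Aim 4 expects the opposite, and section 1.1.b cites 1.8% and 2.0% in one trial and no side effects in two others. Aim 3 assumes STI incidence of 30-40% in controls. That would point the other way, but only if STIs are recorded as AEs.

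**A reader might blame the missed excess wholly on the ever/never measure.** Sixty per arm is also a limit. The rate model itself has only 30-39% power at 0.05 per week. The meaning of a 50% excess matters too. If it means 1.5 times as many participants affected, Fisher power is 32% for 30% versus 45%, 54% for 40% versus 60%, and 76% for 50% versus 75%. The low power applies to an excess in event rate. The study is a pilot and claims no power for AEs.

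**A reader might infer that dropout will make a poorly tolerated product look safe.** With no true difference and 60% retention on kudzu against 90% on placebo, the percentages are 55.5% and 62.4%, and Fisher rejects in 8.2% of trials. That split is a stress case with no source in the documents. At 75% versus 85% the gap is about 2 points and rejection stays below 5%. Section 1.1.b keeps participants who stop study medication in follow-up, and Aim 4 also looks at time to stopping medication.

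**The person-time rate has its own weakness.** If AEs fall mostly in the first weeks, the same 60% versus 90% split gives a false rate ratio of 1.10-1.11 and rejection in 7.5-8.4% of trials, while ever/never stays at 3.5-4.1%. This stands, and it is why the rate should not replace the percentages.

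**On wording,** event rates often means the percentage of participants with an event, so the mismatch with objective 4 is weak by itself. The remark that events are uncommon may refer to individual AE types, for which exact tests are suitable.

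**Conclusion.** The point holds as a gap in the Aim 4 analysis, not as an error in the methods that it names. The single planned summary discards repeat events and observation time, and it comes with no interval. For a 50% higher event rate, under an assumed 0.05-0.2 AEs per person-week, CV 0.5-1.0, 60 per arm and 20% loss, power is about 12-22% for Fisher on ever/never and about 30-80% for an event-rate model. The gain is largest when participants average about one AE or more over 12 weeks and events are not strongly clustered. With rare events it disappears.

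The documents do not support saying that AEs will be common, that exact tests are wrong, or that dropout will hide harm. They do support adding an estimate of the event rate.

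**What to change.** In section 1.7, Aim 4:

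1. Beside the percentages, compare by arm the number of AEs with onset after randomisation and within the 12-week treatment period, per person-week observed. Use a Poisson model with an offset for log weeks observed and participant-level robust standard errors. Report the rate ratio with a 95% CI.
2. Keep percent-with-event and exact tests for individual uncommon AE types and for serious AEs, and name the exact test.
3. State that a non-significant AE comparison does not show tolerability.
4. Reconcile the AE schedule in Table 3 (enrollment and monthly) with the weekly elicitation in section 1.1.c, since this determines what is counted.
5. State that the rate and the percentages are read together, because early clustering of AEs with unequal dropout can bias the rate.

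The cost is a few lines of SAP text and one extra model, from a family already planned for Aims 1 and 3. No new data are needed.
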